### 6.2 Tissue collection

Once a participant is registered, a biopsy site will be identified, and a biopsy will be scheduled. The biopsy sample will be processed per the lab manual. The sample will be sent to City of Hope, where RNA will be extracted. The RNA will be sent to Fulgent Laboratories, which is a CLIA –certified laboratory, for analysis. Residual tissue or RNA will be preserved and stored in the Center for Hope Translational Core Laboratory for correlative studies.

### 6.3 Results and data collection

The assay results from Fulgent will be reported on the SPOCK report form, which will be transmitted to the principal investigator who will ensure copies are given to the treating physician and the data team. The principal investigator will be responsible for linking the participant's study ID on the report form to the participant's identity. The dates on which the biopsy was done and on which the report is given to the treating physician will be recorded.

Participants will be followed every 3 months for up to 3 years to determine length of treatment, reason for discontinuation, and progression free survival.

### 6.4 Duration of Study

Subjects must be withdrawn from the study treatment for the following reasons:

- Subject withdraws consent from the study treatment and/or study procedures. A subject must be removed from the trial at his/her own request or at the request of his/her legally acceptable representative. At any time during the

trial and without giving reasons, a subject may decline to participate further. The subject will not suffer any disadvantage as a result.

- Subject is lost to follow-up.
- Death.

Subjects may be withdrawn from the study for the following reasons:

- The subject is non-compliant with trial procedures.
- If, in the investigator's opinion, continuation of the trial would be harmful to the subject's well-being.

## 7 TOXICITIES AND DOSEAGE MODIFICATION

Because all drugs are FDA-approved for this indication and are being prescribed consistent with their label, the only AEs collected will be those related to the biopsy. Dose modifications will be at the discretion of prescribing physician based on standard practice.

This study will utilize the CTCAE (NCI Common Terminology Criteria for Adverse Events) Version 5.0 for adverse event and serious adverse event reporting. A copy of the CTCAE Version 5.0 can be downloaded: (<http://safetyprofiler-ctep.nci.nih.gov/CTC/CTC.aspx>).

All supportive measures consistent with optimal patient care will be given throughout the study.

## 8 STUDY CALENDAR

### MONTHLY Calendar

Examination	Pre-study  (≤ 28 days of signed consent)	After registration	4-8 weeks after start of therapy 	Every 3 months (+/- 1 month) 	M9D1 (+/- 1 month)	EOT 
Informed consent	X					
Medical history	X					
Eligibility criteria	X					
Vital signs	X	X				
Physical examination	X					X
Study blood tube 		X	X 		X	X
CBC	X					
PT/INR	X					
Biopsy		X	X 			X 
Restaging Scans				X 		X

1 ALL Pre-study/Screening procedures should be completed within 4 weeks of study enrollment - with the exception of laboratory tests which need to be completed within 2 weeks prior to study enrollment.

2 Study blood tube: One lavender top 10 ml tube and one red/gray top 8.5ml tube

3 End of treatment biopsy is optional

4. Restaging scans are recommended to include a chest/abdomen/pelvis CT and either bone scan or PET scan at least every 3 month (+/- 1 month). MRI is an acceptable substitute for CT. After 15 months they can be done at a frequency of the prescriber's discretion.

5. Week 6 blood and biopsy can be done at least 4 weeks and no more than 8 weeks after start of therapy. Start of therapy is defined as the first day of drug taken by the patient after delivery of the biopsy report to the treating oncologist.

## 9 CRITERIA FOR EVALUATION AND ENDPOINT

### 9.1 Efficacy

The following definitions and criteria (RECIST version 1.1)(4) should be used for the baseline evaluations of existing disease, and for the ongoing evaluation of tumor responses.

**Measurable lesions** - lesions that can be accurately measured in at least one dimension with longest diameter (LD)  $\geq 10$  mm using CT, MRI, or caliper measurements or  $\geq 20$  mm with x-ray. Although brain metastases are allowable, no brain lesion will be a TARGET lesion but can be followed as Non-Target.

**Non-measurable lesions** - all other lesions including small lesions (LD  $< 10$  mm with CT, MRI, or caliper measurements or  $< 20$  mm with x-ray).

#### Documentation of “Target” and “Non-Target” Lesions

- All measurable lesions up to a maximum of two lesions per organ and five lesions in total, representative of all involved organs should be identified as *target lesions* and recorded and measured at baseline.
- Target lesions should be selected based on their size (lesions with the longest diameter) and their suitability for accurate repeated measurements (either by imaging techniques or clinical assessments).
- A sum of the LD for *all target lesions* will be calculated and reported as the baseline sum LD. The baseline sum LD will be used as the reference by which to characterize the objective tumor response.
- All other lesions (or sites of disease) should be identified as *non-target lesions* and should also be recorded at baseline. Measurements of these lesions are not required, but the presence or absence of each should be noted throughout follow-up.

##### 9.1.1 Response Criteria

	Evaluation of target lesions
Complete Response (CR)	Disappearance of all target lesions (Must persist for a minimum of four weeks)
Partial Response (PR)	At least a 30% decrease in the sum of the LD of target lesions, taking as reference the baseline sum LD (Must persist for a minimum of four weeks)
Progressive Disease (PD)	At least a 20% increase in the sum of the LD of target lesions, taking as reference the smallest sum LD recorded since the treatment started or the appearance of one or more new lesions
Stable Disease (SD)	Neither sufficient shrinkage to qualify for PR nor sufficient increase to qualify for PD, taking as reference the smallest sum LD since the treatment started

Evaluation of non-target lesions	
Complete Response (CR)	Disappearance of all non-target lesions
Stable Disease (SD)	Persistence of one or more non-target lesion(s)
Progressive Disease (PD)	Appearance of one or more new lesions and/or unequivocal progression of existing non-target lesions

#### 9.1.2 Evaluation of Best Overall Response

The best overall response is the best response observed until progression/recurrence and is determined as indicated in the table below:

Target Lesions	Non-Target Lesions	Evaluation of New Lesions	Best Overall Response
CR	CR	No	CR
CR	SD	No	PR
PR	Non-PD	No	PR
SD	Non-PD	No	SD
PD	Any	Yes or No	PD
Any	PD	Yes or No	PD
Any	Any	Yes	PD

#### 9.1.3 Progression Free Survival

Progression free survival will be determined from the day the biopsy result report is given to the treating oncologist until the date of progression or death, whichever comes first, by RECIST 1.1.

Patients who have not progressed or died at the time of analysis will be censored at the time of the latest date of assessment from their last evaluable RECIST v1.1 assessment.

For the primary analysis, patients who change therapy for reasons other than RECIST 1.1 progression will be censored at the time of starting new therapy, but a sensitivity analysis will be performed counting these as progression events. Patients who continue on therapy at the discretion of the treating oncologist but who have progression by RECIST 1.1 will be considered to have progressed and will have end of treatment (EOT) procedures done.

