#### 1.1.2 Primary Endpoint

Progression free survival in patients treated in concordance with recommendation

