## 6 TREATMENT PLAN

### 6.1 Patient enrollment

Once a patient signs the informed consent form, she/he may be screened. If all inclusion/exclusion criteria are met, then they are enrolled. During screening a biopsy site will be identified. In accordance with the ASCO Ethical Framework for Mandatory Research Biopsies, because the biopsy results are used in the primary endpoint of the study, the biopsy risk may be low or moderate risk (expected rate of major complications < 1.5%), including biopsy of bone marrow, skin, superficial masses, intra-abdominal masses, peripheral thoracic masses that can be accessed without penetrating lung, or sites that will be biopsied for other clinical purposes.

Note that after patients may be continued on the most recent therapy up to the biopsy at the discretion of the treating oncologist. After the biopsy, the treating oncologist may opt to start a new therapy while waiting for results and then switch based on results if desired. No wash-out period necessary.

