## **10 STATISTICAL CONSIDERATIONS**

### **10.1 Sample size determination**

This is an open-label phase II study of systems biology guided therapy for breast cancer patients positive for Oestrogen receptor after Aromatase inhibitor and CDK inhibition. Based on the SOLAR-1 trial, 25% of tumors would have PIK3CA mutation, so 25% of people would be treated with fulvestrant plus alpelisib with a median PFS in that group of 11 months and 75% of people would be treated with fulvestrant with a median PFS in that group of 6 months.(3) The weighted average of these medians is 7.25 months, but since the actual distributions of the progression free survivals are not available, we will use a conservative estimate of the expected median PFS of the historical control group (fulvestrant +/- alpelisib as second line unguided therapy) of 8 months.

Based on the preclinical assessments and assay features, it is expected that 10% of patients enrolled in the trial will be assigned to capecitabine, 25% to fulvestrant/alpelisib, 32.5% to fulvestrant, and 32.5% to exemestane everolimus. The goal is to assign people to therapy so that the capecitabine group will have a median PFS of 18 months (75th percentile of survival in BOLERO-6(5)), the fulvestrant group will have a median PFS of 10 months (75th percentile of survival in SOLAR-1(3)), and the exemestane/everolimus group will have a median PFS of 13 months (25th percentile of BOLERO-2(6)). From the results of the BOLERO-2 trial, BOLERO-6 trial, and the SOLAR-1 trial, it is hypothesized that the weighted median PFS with genomic- guided therapy will be improved to 12.1 months from 9 months of fulvestrant +/- alpelisib as second line unguided therapy after AI+CDK inhibitor.

With an alpha of 0.1, beta of 0.2, 18 months of accrual, and 6 months of follow-up, 66 patients are needed to detect a 4-month improvement in the median PFS (from 8 months to 12 months) with genomic- guided therapy, assuming an exponential distribution using a 2-sided Log-rank test. Accounting for 10% loss, the trial will enroll 74 eligible patients.

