## 10.2 Statistical Analysis

### 10.2.1 Primary Endpoint

#### **Progression Free Survival (PFS)**

PFS is defined as the time from the time results are given to the treating oncologist to the first occurrence of disease progression or death from any cause (whichever occurs first) according to RECIST 1.1. Patients without disease progression or death at the time of analysis will be censored at the last disease assessment date from their last evaluable RECIST v1.1 assessment.

For the primary objective, all enrolled patients who receive therapy concordant with the genomic recommendation will be evaluable for analysis. Concordant therapy will be any anti-estrogen plus any PI3K inhibitor in the “fulvestrant plus alpelisib” group, any anti-estrogen plus any MTOR inhibitor in the “exemestane plus everolimus” group, any antiestrogen in the “fulvestrant” group, and any cytotoxic chemotherapy in the “capecitabine” group.

The PFS curve will be estimated using the Kaplan-Meier product-limit method. Two-sided, 95% CI for the median PFS will be computed by the Brookmeyer and Crowley method with log-log transformation.

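### The therapy-change rule in Section 9.1.3 does not exempt the results-based switch from interim therapy that Section 6.1 permits

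*Combined protocol and SAP*

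**What the plan says.** Section 6.1 allows treatment between biopsy and report. Of the oncologist it says: "may opt to start a new therapy while waiting for results and then switch based on results if desired". No wash-out is required.

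Section 9.1.3 starts the PFS clock on the day the report is given to the treating oncologist. Its rule for the primary analysis reads: "patients who change therapy for reasons other than RECIST 1.1 progression will be censored at the time of starting new therapy". The rule has no exception. The same sentence then adds a second analysis of these patients: "but a sensitivity analysis will be performed counting these as progression events". The section dates the censoring, but it gives no event date for the sensitivity analysis.

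The primary endpoint in Section 1.1.2 is "Progression free survival in patients treated in concordance with recommendation". Section 10.2.1 says that "all enrolled patients who receive therapy concordant with the genomic recommendation will be evaluable for analysis" and defines concordance by drug class, for example "any antiestrogen in the “fulvestrant” group". It repeats the PFS definition but does not mention therapy changes. The secondary PFS comparison in Section 10.2.2 (concordant against discordant patients) reuses the same PFS definition.

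Footnote 5 of the Section 8 calendar adds: "Start of therapy is defined as the first day of drug taken by the patient after delivery of the biopsy report". It does so to time the week 6 blood and biopsy.

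**The concern.** A switch prompted by the report happens on or after time zero and is not made for RECIST 1.1 progression. It therefore meets the literal terms of the therapy-change rule. The drug that makes the patient evaluable under 10.2.1 also ends her follow-up in the primary analysis, and the sensitivity analysis counts starting it as failure.

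Two things are at stake. The primary analysis would lose these patients' follow-up on the therapy under test. The sensitivity analysis could not check the primary result, because it would mix real treatment failures with patients who simply followed the recommendation. An analyst who sees the problem would have to supply an unwritten exemption after open-label outcomes are known.

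**Working it through.** **The text, step by step.**
1. Interim therapy followed by a switch is permitted (6.1).
2. Time zero is report delivery, so the switch cannot precede it (9.1.3).
3. The reason for the switch is the report, not RECIST 1.1 progression, so the rule applies (9.1.3).
4. The patient is in the primary analysis because of the drug she switched to (1.1.2, 10.2.1).
5. No exemption appears in 9.1.3, 10.2.1 or the calendar. Footnote 5 is not cited by the PFS rule and is not tied to the recommended drug. A patient still taking the interim drug after the report has already started therapy under it.

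**Who is affected.** Only patients whose interim drug is not already concordant. Section 10.1 expects 10% assigned to capecitabine and "25% to fulvestrant/alpelisib, 32.5% to fulvestrant, and 32.5% to exemestane everolimus". If the interim drug is an antiestrogen alone (assumed), the 32.5% in the fulvestrant group need no switch and 67.5% do. Adding a partner drug is treated here as a change; the documents do not say.

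**The plan's own figure.** Inputs from 10.1: median 8 against 12 months, exponential, two-sided alpha 0.1, power 0.8, 18 months accrual, 6 months follow-up.
- Hazard at a 12-month median: λ = ln 2 / 12 = 0.05776.
- Event probability: 1 − (e^(−6λ) − e^(−24λ)) / (18λ) = 1 − (0.7071 − 0.2500) / 1.0397 = 0.560.
- One-sample log-rank with variance equal to expected events. Per patient, expected null events are 1.5 × 0.560 = 0.8405, and the difference from observed is 0.8405 − 0.5604 = 0.2802. N = (1.645 + 0.842)² × 0.8405 / 0.2802² = 66.2.
- Log-hazard formula: (1.645 + 0.842)² / (ln 1.5)² = 37.6 events, and 37.6 / 0.560 = 67.1.

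Both agree with 66 to within rounding and choice of method. With 10% loss, 66 / 0.9 = 73.3, rounded up to 74. About 66 × 0.560 = 37 events are expected.

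**Effect of the rule as written.** The switch share f is an assumption throughout. Switchers are random with respect to prognosis.
- Sensitivity median, taking the event at the start of the new drug, close to time zero: (1 − f) e^(−λt) = 0.5, so t = 12 × ln(2(1 − f)) / ln 2. At f = 10%: 12 × 0.5878 / 0.6931 = 10.2 months.
- Primary power: 40,000 simulated trials per setting, n = 66, switch at 0.25 months, one-sided 5% (equal to two-sided 0.1). The range covers two variance choices for the one-sample log-rank test and, within rounding, an exponential-rate Wald test.
- Closed-form check: Φ(√D × ln 1.5 − 1.645) with D = 66(1 − f) × 0.560.

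| f (assumed) | Switchers of 66 | Sensitivity median, months | Mean primary events | Power, simulated | Power, closed form |
|---|---|---|---|---|---|
| 0 | 0 | 12.0 | 37.0 | 82–84% | 79% |
| 5% | about 3 | 11.1 | 35.2 | 80–83% | 78% |
| 10% | about 7 | 10.2 | 33.4 | 78–81% | 76% |
| 20% | about 13 | 8.1 | 29.8 | 73–77% | 71% |

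The sensitivity median equals the 8-month reference when f = 1 − 0.5 × 2^(8/12) = 20.6%. With the 10.1 mix and 10% of patients starting interim therapy (assumed), f = 0.675 × 10% = 6.75%, which gives a sensitivity median of 10.8 months and power of 79–82%.

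Simulated type I error at a true median of 8 months was 4.0–5.3% for f from 0 to 30%. In a separate run of 20,000 trials per setting, the typical primary Kaplan-Meier median (computed on 2,000 of them) stayed close to 12 months. Moving the switch between 0 and 1 month changed power by at most about 2 points.

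**The case against.** The strongest reply is that the context shows what was meant. The Study Summary gives treatment until intolerance or progression. Section 6.3 follows patients for length of treatment and reason for stopping. The sentence after the disputed one in 9.1.3 deals with patients who stay on therapy and with end-of-treatment procedures. Footnote 5 ties the start of therapy to the report. In that setting, a change of therapy naturally means leaving the post-report treatment. This stands as evidence of intent, but it does not settle the text: 6.1 itself calls the interim drug a new therapy, and footnote 5 only times samples.

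Three further points stand. Every switch share and switch date is assumed, so the 20% row shows direction and is not a forecast. The sensitivity event date is inferred; the start of the new drug is the natural reading. The log-rank test appears for this endpoint only in the sizing of 10.1, while 10.2.1 plans a Kaplan-Meier curve and a confidence interval for the median, so the power figures illustrate lost information.

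A reader might infer more than the documents support:
- That the primary result is biased or its error rate inflated. The calculation shows neither if switching is unrelated to prognosis. If it is related, the censoring would be informative, but the documents give nothing from which to judge this.
- That 9.1.3 and 10.2.1 contradict each other. Section 10.2.1 is silent on therapy changes.
- That 66 and 74 are wrong. They reproduce.
- That every interim start is caught. An interim drug already in the concordant class involves no switch.

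**Conclusion.** The gap is real and should be closed: a stated rule, followed literally, ends follow-up on the recommended therapy when it starts, or scores that start as progression. The missing exemption is certain from the text; the size is not, because the share who switch is unknown. At an assumed 5–10% the primary analysis loses roughly 2 to 4 points of power, mainly a matter of precision. The sensitivity median drops by about 1 to 2 months from a true 12, and larger shares cost more. These figures assume exponential PFS, early switches unrelated to prognosis, and the sensitivity event dated at the start of the new drug.

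**What to change.** State in 9.1.3 that the first results-based change from interim therapy to the post-report therapy, whether concordant or discordant, is not a change of therapy for the censoring rule or the sensitivity analysis, and that the rule applies only to later changes. State the event date for the sensitivity analysis. Refer to 9.1.3 from 10.2.1.

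The exemption must apply identically to both groups in the 10.2.2 comparison. If only switches to concordant therapy were exempt, a discordant patient who left an interim drug for another non-recommended drug would still be censored, or counted as failed, near day zero. In the sensitivity version that would favour concordance.

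Prespecify a window after report delivery within which a switch counts as this first change. Otherwise a patient who does well on interim therapy and switches late would have that event-free time credited to the recommendation. The window is an analysis rule and does not restrict treatment; its length is for the sponsor to choose.

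The cost is a few sentences and one cross-reference. The report date is already collected under 6.3, but the start date of the post-report therapy must be recorded separately from that of any interim drug. The sample size of 66 evaluable and 74 enrolled does not change.

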**Name of Institution**

## STUDY SUMMARY

Title	Systems Biology Guided Therapy for Breast Cancer Positive for Oestrogen Receptor after Aromatase Inhibitor and CDK inhibition.
Short Title	SPOCK
Protocol Identifiers (IRB – internal)	U21-02-4401
IND number	N/A
Phase	II
Design	
Open label, interventional
 
All patients will have a biopsy at the beginning of the trial. The biopsy will be sent for DNA sequencing through FoundationOne (clinical test) and RNA profiling at Fulgent (research test) for determination of activation of various oncogenic pathways and phenotypes. The results will be analyzed by [name] and [name], and a treatment recommendation will be made to the treating physician based on the algorithm below.
 
Biopsies will also be performed 2-4 weeks after the start of therapy for correlative purposes.

Study Duration	24 months recruitment, with up to 3 years of follow up per patient
Objectives	
Primary To determine if systems biology guided therapy can improve PFS
 
Secondary To determine the minimum turn-around time needed for systems biology analysis
 
To determine the response rate to systems biology guided therapy
 
To compare PFS based on concordance with recommended treatment

Number of Subjects	74 treated according to recommendations
Diagnosis and Main Eligibility Criteria	
 
• Metastatic or incurable breast cancer
 
• Progression while on aromatase inhibitor and CDK inhibitor
 

	
 
• Biopsiable lesion
 
• ECOG 0-2
 
• Age 18 or greater
 

Study Product, Dose, Route, Regimen	Drug determined by treating oncologist based on recommendation from systems biology analysis.
Duration of administration	Until intolerance or progression.
Reference therapy	Unguided therapy
Statistical Methodology	The PFS will be compared to 8 months, which is the approximate expected median PFS of fulvestrant +/- alpelisib as second line unguided therapy after AI+CDK inhibitor based on SOLAR-1. With a two-sided alpha of 0.1, beta of 0.2, 18 months of accrual, and 6 months of follow-up, 74 patients are needed to detect a 4 month improvement in PFS with genomic - guided therapy.

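### The primary PFS analysis censors every non-RECIST therapy change, including any made for clinical progression, and Section 10.2.1 carries neither the rule nor its sensitivity analysis

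*Combined protocol and SAP*

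**What the plan says.** Section 9.1.3 starts PFS when the biopsy report reaches the treating oncologist. Patients without an event are censored at their last evaluable RECIST assessment. For the primary analysis it adds that "patients who change therapy for reasons other than RECIST 1.1 progression will be censored at the time of starting new therapy". The same sentence says that "a sensitivity analysis will be performed counting these as progression events".

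Section 10.2.1 defines PFS again for the analysis. Its only censoring rule is "Patients without disease progression or death at the time of analysis will be censored at the last disease assessment date". It does not mention therapy changes or the sensitivity analysis. Its stated method is Kaplan-Meier estimation with an interval: "Two-sided, 95% CI for the median PFS will be computed by the Brookmeyer and Crowley method with log-log transformation".

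The comparison itself stands elsewhere. The Study Summary says "The PFS will be compared to 8 months". Section 10.1 gives the design: "With an alpha of 0.1, beta of 0.2, 18 months of accrual, and 6 months of follow-up, 66 patients are needed", for an improvement "from 8 months to 12 months", with an exponential model and a two-sided log-rank test.

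On treatment before the report, Section 6.1 says that "the treating oncologist may opt to start a new therapy while waiting for results and then switch based on results if desired".

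**The concern.** The rule does not look at why therapy changed. A patient switched for toxicity and a patient switched because the disease is clearly worsening are both censored. For the second patient the censoring is informative, because that patient was about to have an event. This can plausibly happen here. The trial is open label and the treating oncologist chooses therapy. Scans are about 3 months apart (+/- 1 month), and after 15 months their frequency is at the prescriber's discretion (Section 8, footnote 4). Measurable disease is not an inclusion criterion (Section 5.1).

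In a randomised trial a comparator might share the bias. Here there is one arm and a fixed 8 months, so any lengthening of apparent PFS counts directly towards success.

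Two smaller points go with this. Switchers are credited with time up to the start of new therapy, which may be unassessed, while all other patients are credited only to their last evaluable assessment. And an analyst working from Section 10.2.1 alone would not censor at a switch, and would count a later RECIST progression or death.

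**Working it through.** **1. The plan's own figure.** Inputs from Section 10.1: medians 8 and 12 months, two-sided alpha 0.10, power 0.80, accrual 18 months, follow-up 6 months. With rate λ = ln 2 / median and uniform accrual,

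P(event) = 1 − [exp(−6λ) − exp(−24λ)] / (18λ),

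which is 0.699 at median 8 and 0.560 at median 12.

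- Log-hazard-ratio form: (1.645 + 0.842)² / (ln 1.5)² = 37.6 events; 37.6 / 0.560 = 67.1, so 68.
- One-sample log-rank form: 65.5, so 66, the plan's figure.
- With 10% loss: 66 / 0.9 = 73.3, so 74.
- Simulated power at 66 patients and a true median of 12 months: 0.82.

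The design reproduces. The sample size is not in question.

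**2. Hand check of the bias.** Take a true median of 8 months and let a share f of progressions be censored as therapy changes at about the time they occur. The apparent median becomes about 8 / (1 − f): 8.4, 8.9 and 10.0 months at f = 5, 10 and 20%. Expected events are 66 × 0.699 = 46.1. The statistic Z = (O − E) / √E shifts by about −f × √46.1 = −6.79f, that is −0.34, −0.68 and −1.36. The chance of Z < −1.645 is then roughly Φ(−1.305) = 0.10, Φ(−0.965) = 0.17 and Φ(−0.285) = 0.39, against a nominal 0.05.

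**3. Simulation.** 66 patients, exponential PFS with median 8 months, 18 + 6 months, one-sample log-rank, success if Z < −1.645. The share is an assumption, as the documents give none.

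| Benefit-side error | 0% | 5% | 10% | 20% |
|---|---|---|---|---|
| Censored, switch 0–1 month before RECIST progression | 4% | 8% | 14% | 36% |
| Censored, switch at the time of progression | 4% | 8.5% | 15% | 38% |
| Censored, switch 2 months before | 4% | 8% | 13% | 30% |
| Same patients counted as events, no lag | 4% | 4% | 4% | 4% |
| Switches unrelated to prognosis, censored | 4% | 4% | 4% | 4% |

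If success is instead a 95% Brookmeyer-Crowley lower limit above 8 months, the error is 2% with no clinical switchers, 7% at a 10% share and 17% at 20% (censored at the time of progression).

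**4. The planned sensitivity analysis.** It counts every change as progression, including those for toxicity or preference. If all changes are unrelated to prognosis, it lowers the benefit-side error to 2% at a 5% share and below 1% from 10%. In a mixed case (assumed 10% clinical and 10% unrelated, the unrelated switch times exponential with median 8 months):

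- Primary rule: error 14.9%.
- All changes as events: error 1.3%, and power at a true 12 months falls to 63%.
- Only clinical progressions as events, other switchers followed on: error 3.9%, power 81%.

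Censoring the unrelated switchers instead should give much the same error, because the last row of the table shows that censoring them does not inflate it. The two planned analyses therefore lie on opposite sides of the rule that separates the reasons.

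**The case against.** A reader might infer that the 8-month null will be rejected too often. The documents do not support that as a fact. They give no share of changes made for clinical progression, and changes unrelated to prognosis cause no inflation. Several provisions also limit the harm:

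- The study calendar schedules restaging scans at end of treatment, so a deteriorating patient is due a scan around the switch. If those scans documented progression in half of such patients (assumed), the error at 10% and 20% falls to about 8% and 14%.
- Section 9.1.1 counts new lesions and unequivocal non-target progression.
- The sensitivity analysis is in the same sentence as the rule and is the opposite bound.
- Section 10.1 calls 8 months conservative against its weighted 7.25. With a true median of 7.25 the error is about 2, 4 and 16% at 5, 10 and 20%. That margin is uncertain, since Section 10.1 also mentions 9 months, and nothing says how the historical figure was censored.

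A reader might also infer that the gap in Section 10.2.1 causes the bias, or that the plan prescribes two contradictory primary analyses. It does neither. Section 9.1.3 expressly names the primary analysis and Section 10.2.1 is silent, so the two can be read together. The gap is a separate inconsistency.

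A third tempting reading is that a planned move from interim to recommended therapy censors the patient near day 0. The wording of Section 9.1.3 leaves room for it, but footnote 5 of the study calendar dates start of therapy from the first drug taken after the report is delivered, so the reading is weak.

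Finally, following patients past a switch would credit later drugs to the guidance. That is a different estimand, and it is not needed here. What stands is that the primary rule ignores a reason the trial already records, and that the error it can introduce favours success.

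**Conclusion.** The concern holds as potentially informative censoring of unknown size, in one direction, against a fixed benchmark. At an assumed 5, 10 or 20% share of clinical switchers the benefit-side error goes from about 4% to about 8, 14 or 36%. This rests on exponential PFS, a true median of 8 months, a one-sample test at z = 1.645 and no rescue by end-of-treatment scans. Under the interval criterion the inflation is about half as large. Section 10.2.1 states no formal rejection rule, so the exact figure depends on which criterion is applied. The different censoring date for switchers and the omission from Section 10.2.1 are plain on the text and need no assumption. Severity: should fix.

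**What to change.** 1. In the primary analysis, count a therapy change for documented clinical progression as a PFS event, with a written definition, using the reason for discontinuation collected under Section 6.3. At minimum, add this as a named sensitivity analysis beside the existing one.
2. Censor the remaining non-progression changes at the last evaluable assessment before the switch, as for all other patients.
3. Put the identical rule and all sensitivity analyses in Section 10.2.1.
4. State that moving from interim therapy (Section 6.1) to the recommended therapy after the report is the start of study therapy, as in footnote 5 of the study calendar, and not a change of therapy under Section 9.1.3.

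The cost is protocol and SAP wording, since the reason is already collected. Reported PFS may be slightly less favourable. Clinical progression is judged by the investigator in an open-label trial, which is why it needs a stated definition and why the existing sensitivity analysis should stay.
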